**Figure 4: Schematic of the LUMINIZE Study Design****5.8. SUBJECT SELECTION**

Subjects will be recruited from the investigator's general patient population. Subjects considered for participation in this study will be entitled to undergo a standard-of-care ablation, LAA or ASD closure procedure. It is the site's responsibility to verify the subject's eligibility for participation in the trial. A subject is considered as enrolled once the study-specific Informed Consent Form is signed.

An overview of the in-and exclusion criteria is listed in Table 2 below.

Table 2: In-and Exclusion Criteria for the LUMINIZE Study

**LUMINIZE_CLINICAL PROTOCOL**Document ID: VER-DOC-527
Controlled Document: VER-SIGN-3084TEMPLATE:
ONEPROJECTS/SIGN-267

Version: 4.0

Project: VERAFYE (VER)
Date: 22-Nov-2024 14:16:10
Page: 19 / 51**Inclusion Criteria**

IC1: Subject is 18 to 80 years of age at the time of consent

IC2: Subject is scheduled to undergo a standard of care*, de-novo

- catheter-ablation procedure to treat typical AFL or AF

or

- left atrial appendage (LAA) closure procedure

or

- atrial septal defect (ASD) closure procedure

*according to current international and local guidelines and currently approved indications

IC3: Subject is able to understand and willing to provide written informed consent

IC4: Subject is able and willing to complete all study assessments

Exclusion Criteria

EC1: Any of the following within 6 months prior to enrolment:

- Cardiac surgery including coronary artery bypass grafting, ventriculotomy, atriotomy
- Thromboembolic event (stroke), transient ischemic attack (TIA) or neurological disturbances
- Myocardial infarction
- Any surgical or percutaneous cardiac procedure including coronary intervention and cardiac ablation
- Dilated or hypertrophic cardiomyopathy

EC2: Any planned surgical or endovascular intervention within 30 days before or after the ablation, or LAA/ASD closure procedure.

EC3: Any of the following cardiac conditions:

- New York Heart Association (NYHA) class IV

**LUMINIZE_CLINICAL PROTOCOL**Document ID: VER-DOC-527
Controlled Document: VER-SIGN-3084TEMPLATE:
ONEPROJECTS/SIGN-267

Version: 4.0

Project: VERAFYE (VER)
Date: 22-Nov-2024 14:16:10
Page: 20 / 51

- Left ventricular ejection fraction (LVEF) < 30%
- Implanted with a cardiac rhythm management device (pacemaker, CRT, ICD, loop recorder)
- Presence of intramural thrombus, tumor, or other abnormality that precludes vascular access, catheter introduction, or manipulation
- Active coronary ischemia, significant valvular heart disease, or hemodynamically significant congenital cardiac abnormality

EC4: Body mass index (BMI) > 40 kg/m²

EC5: Body weight < 50kg

EC6: Pregnant women or women who plan to become pregnant during the course of their participation in the study (women should either be of non-childbearing potential at the time of enrolment (as documented in the medical file) or have a negative pregnancy test within the previous 7 days prior to the ablation, or LAA/ASD closure procedure)

EC7: Life expectancy less than 12 months

EC8: Subjects who are currently enrolled in another study

Imaging Exclusion Criteria

IEC1: Subjects with a thrombus or pericardial effusion detected in the LA/LAA during standard of care imaging.

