5.1. CONTACT INFORMATION

Position	Details
Sponsor	LUMA Vision Ltd. [name]
Coordinating Principal Investigator	[name]. [name] [name], FESC, FEHRA Mater Private Network Heart & Vascular Centre [name]

**LUMINIZE_CLINICAL PROTOCOL**Document ID: VER-DOC-527
Controlled Document: VER-SIGN-3084TEMPLATE:
ONEPROJECTS/SIGN-267

Version: 4.0

Project: VERAFYE (VER)
Date: 22-Nov-2024 14:16:10
Page: 7 / 51

	Ireland Email: [contact]
Clinical Manager	[name] [contact] [contact]
Clinical Research Engineer	[name] [contact] [contact]

5.2. PROTOCOL SYNOPSIS**Study title:** LUMINIZE: Luma Vision's feasibility study on the VERAFEYE system**Study Objective:** The objective of the study is to collect data on the usability and integration of the VERAFEYE System in

- standard of care catheter-based ablation treatments for Typical Atrial Flutter (AFL) or Atrial Fibrillation (AF)
- standard of care left atrial appendage (LAA) closure procedures
- standard of care atrial septal defect (ASD) closure procedures

Results from this study will be used to guide development and refinement the VERAFEYE System.

Indication for Use: The VERAFEYE System is indicated for intracardiac and intraluminal ultrasound visualization of cardiac and great vessel anatomy and physiology as well as visualization of other devices in the heart and great vessels of patients.**Clinical Investigation Device:** VERAFEYE System, comprising of

- **VIC** - VERAFEYE Imaging Catheter
- **CIU** - Catheter Interface Unit
- **SC** – System Console

Control Device: NA**Study Design:** The LUMINIZE study is a prospective, non-randomized, single-arm feasibility study.

**LUMINIZE_CLINICAL PROTOCOL**Document ID: VER-DOC-527
Controlled Document: VER-SIGN-3084TEMPLATE:
ONEPROJECTS/SIGN-267

Version: 4.0

Project: VERAFYE (VER)
Date: 22-Nov-2024 14:16:10
Page: 8 / 51

Planned Number of Subjects: Enrolment will be considered as complete when 40 subjects have completed the ablation, or LAA/ASD closure procedure with the VERAFYE System as imaging system.

Planned Number of Sites/Countries: Up to 2 sites in Ireland may participate in this study.

Study Endpoints: This is a feasibility study and no formal endpoints or hypothesis testing are planned in the study. The study is not designed to collect data for product approval and as such does not have a safety or efficacy endpoint.

Inclusion Criteria:

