5.5. STUDY OBJECTIVE

The objective of the study is to collect data on the usability and integration of the VERAFEYE System in standard of care

- catheter-based ablation treatments for Typical Atrial Flutter (AFL) or Atrial Fibrillation (AF)
- left atrial appendage closure (LAAC) procedures
- atrial septal defect (ASD) closure procedures

Results from this study will be used to guide development and refinement the VERAFEYE System.

**LUMINIZE_CLINICAL PROTOCOL**Document ID: VER-DOC-527
Controlled Document: VER-SIGN-3084TEMPLATE:
ONEPROJECTS/SIGN-267

Version: 4.0

Project: VERAFEYE (VER)
Date: 22-Nov-2024 14:16:10
Page: 17 / 51**5.6. STUDY ENDPOINTS**

This is a feasibility study and no formal endpoints or hypothesis testing are planned in the study. The study is not designed to collect data for product approval and as such does not have a safety or efficacy endpoint.

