5.7. STUDY DESIGN

This is a prospective, non-randomized, single-arm feasibility study. This study is a pilot stage study according to ISO/FDIS 14155: 2020 (E) - Annex I. Results from this study will be used to guide development and refinement of the VERAFEYE System.

The study is designed to assess the usability and integration of the VERAFEYE System in standard of care, catheter-based ablation treatments for Typical Atrial Flutter (AFL) or Atrial Fibrillation (AF), standard of care left atrial appendage closure (LAAC) procedures and standard of care atrial septal defect (ASD) closure procedures. Results from this study will be used to guide development and refinement the VERAFEYE System.

Intended Users of the VERAFEYE System are interventional cardiologists and electrophysiologists who are trained in percutaneous and transseptal procedures and who have completed the VERAFEYE System training. The VERAFEYE System training is offered by the Sponsor. The VERAFEYE System should only be performed by these Intended Users.

A prospective study design will ensure that identical procedures are followed for data capture and review.

Up to 4 operators per site will be allowed to perform study procedures, unless written approval from LUMA Vision was obtained.

A sample size of 40 subjects was chosen to allow for sufficient feasibility testing and data collection for the ablation, LAA and ASD closure procedures. The sample size is not statistically based but is based on a reasonable number of data sets to assess the images collected with the VERAFEYE System.

In protocol rev 4.0, the sample size was extended from 20 subjects to 40 subjects, in order to collect more clinical data for further system development and to ensure the collection of information from different operators.

Enrolment in this study is competitive, there is no limit of enrolments per site.

Subject procedures will follow a sequential pattern (one site after the other) to allow LUMA Vision field support personnel to be present during the procedures and to ensure the availability and installation of necessary equipment.

[figure not shown]
Enrolment in the study is expected to be completed in approximately 6 months. The follow-up for each participant is expected to be approximately 7 days, therefore the total study duration is expected to last approximately 7 months.

**LUMINIZE_CLINICAL PROTOCOL**Document ID: VER-DOC-527
Controlled Document: VER-SIGN-3084TEMPLATE:
ONEPROJECTS/SIGN-267

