5.9.2. SUBJECT CLASSIFICATION

- Enrolled subject- Any participant who signs the informed consent form.
- Screen Failure subject- Any participant who signs the consent form but is found to not meet eligibility criteria.
- Intent subject- Any participant who signs the consent form, met the eligibility criteria but did not have the VERAFEYE Imaging Catheter inserted into the body.
- Attempt subject- Any participant who signs the consent form, met the eligibility criteria, did have the VERAFEYE Imaging Catheter inserted into the body but did not undergo the ablation/LAA/ASD closure procedure per this study protocol.
- Procedure subject - Any participant who undergoes the ablation/LAA/ASD closure procedure with the VERAFEYE System as imaging system per this study protocol.

These subjects are followed in accordance with the Follow-Up schedule and data will be included in all study analyses.

[figure not shown]
- Withdrawn subject - A participant who chooses to or is withdrawn from the study.
- Lost-to-follow up subject - A participant who cannot be reached anymore after 3 attempts.

Enrolment will be considered as complete when 20 procedure subjects have been enrolled.

The Figure below shows the subject classifications.

**LUMINIZE_CLINICAL PROTOCOL**Document ID: VER-DOC-527
Controlled Document: VER-SIGN-3084TEMPLATE:
ONEPROJECTS/SIGN-267

Version: 4.0

Project: VERAFYE (VER)
Date: 22-Nov-2024 14:16:10
Page: 22 / 51**Figure 5: Subject Classifications****5.9.3. END OF STUDY**

Individual study subject participation will end when the last subject follow-up visit is completed; when the subject withdrew or was withdrawn from the study or when the subject is considered as lost-to-follow up.

The study will be considered as complete when the last subject's follow up visit occurs or when subjects are no longer being considered for participation. Routine management and standard practice of care will continue for the subjects who have completed the study.

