- insurance coverage for subjects in the study was obtained
- EC approval was obtained

It is the responsibility of the Principal Investigator to

- ensure that no deviations from this protocol occur, except if considered as needed to protect the life and physical well-being of a subject in an emergency. Any deviations that occurred during the study need to be documented, together with a rationale for the deviation.
- ensure that source documents and essential study documents throughout the clinical study are maintained and retained per requirements.
- ensure that the accuracy, completeness, legibility, and timeliness of the data reported to the sponsor in the CRFs and in all required reports
- record, report, and assess every adverse event as applicable per the protocol and observed device deficiency.
- report to sponsor, per the protocol requirements, all reportable events
- report to the EC and regulatory authorities any SAEs and device deficiencies that could have led to a SADE and potential UADE or USADE, as required by local/regional regulations
- maintain the device accountability records and control of the devices
- ensure that adequate facilities are available to perform the study
- ensure that informed consent is obtained in accordance with applicable laws, this protocol and local EC requirements (see section 21.4)
- allow the sponsor to perform monitoring and auditing activities.

**LUMINIZE_CLINICAL PROTOCOL**Document ID: VER-DOC-527
Controlled Document: VER-SIGN-3084TEMPLATE:
ONEPROJECTS/SIGN-267

Version: 4.0

Project: VERAFYE (VER)
Date: 22-Nov-2024 14:16:10
Page: 43 / 51

- regulatory authorities and ECs to perform auditing activities.

The Principal Investigator or his/her designee will take measures to prevent accidental or premature destruction of these documents.

5.14.2.0.4.1. Delegation of Responsibilities

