5.14.8. PROTOCOL DEVIATIONS

No deviations from the protocol are allowed, except to protect the rights, safety, and well-being of human subjects under emergency circumstances. In that event, the Investigator will notify Sponsor immediately in writing. The Investigator will also inform their EC of all deviations according to Institutional requirements. In the event of any deviation from the clinical protocol, a deviation CRF will be completed. The occurrence of clinical investigation plan deviations will be monitored by the Sponsor on an ongoing basis.

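### For a congenital ASD judged hemodynamically significant, the defect that qualifies the subject under IC2 also excludes the subject under EC3

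*Combined protocol and SAP*

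**What the plan says.** ASD closure is one of the procedures the study is meant to cover. The synopsis objective lists "standard of care atrial septal defect (ASD) closure procedures", Section 5.5 repeats "atrial septal defect (ASD) closure procedures", and Section 5.7 says the 40 subjects were chosen "to allow for sufficient feasibility testing and data collection for the ablation, LAA and ASD closure procedures". Section 5.10.3.3 gives ASD closure its own list of recommended views.

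IC2 (Table 2 in Section 5.8, and the synopsis in Section 5.2) accepts a subject scheduled for a standard-of-care "atrial septal defect (ASD) closure procedure". It sets no condition on the origin or hemodynamic importance of the defect. Its footnote refers to guidelines and approved indications, which the protocol does not reproduce.

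EC3 excludes a subject who has any one of a list of cardiac conditions. The last item, worded identically in Table 2 and the synopsis, is "Active coronary ischemia, significant valvular heart disease, or hemodynamically significant congenital cardiac abnormality".

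Three other provisions decide what follows:

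- Section 5.9.2 defines a screen failure as "Any participant who signs the consent form but is found to not meet eligibility criteria".
- Section 5.14.8 states "No deviations from the protocol are allowed, except to protect the rights, safety, and well-being of human subjects under emergency circumstances".
- Section 5.14.2 makes it the principal investigator's duty to "ensure that no deviations from this protocol occur".

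**The concern.** An exclusion criterion normally removes a subject for something other than the indication under study. Here, for one type of ASD candidate, the indication is itself the ground for exclusion, and the text does not show whether that was intended.

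Two things are at stake:

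- **Who enters for ASD closure.** A site that applies EC3 literally turns away subjects whom the objective and the sample-size rationale say the study should observe.
- **Avoidable eligibility deviations.** A site that assumes the index defect is exempt enrols against a written exclusion, in a protocol that permits deviations only in emergencies.

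Up to two sites enrol competitively, and Section 5.8 leaves verification of eligibility to the site. The same criterion could therefore be applied differently at each.

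**Working it through.** No formula in the plan bears on this point, so the check compares the criteria.

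**1. Apply both criteria to each kind of index ASD.** The EC3 column concerns the congenital item only; every other criterion still applies.

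| Index ASD | IC2 | EC3, congenital item |
|---|---|---|
| Congenital, judged hemodynamically significant | met | met: excluded |
| Congenital, judged not significant | met | not met |
| Not congenital | met | not met |

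The conflict is confined to the first row. The third row is not empty on the protocol's own account, since Table 4 (Section 5.11.3) lists residual ASD among the adverse events of ablation. EC1 narrows that row, because a cardiac ablation in the 6 months before enrolment excludes the subject on a separate ground.

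**2. Look for text that resolves the first row.** The EC3 item appears twice (synopsis and Table 2).

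- Exemptions for the defect being closed: 0.
- Definitions of hemodynamically significant: 0.
- Statements on how EC3 applies to ASD candidates: 0.

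The preceding EC3 item, on thrombus, tumor or other abnormality, is limited to what would prevent vascular access or catheter handling. The congenital item carries no such limit.

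**3. Follow a first-row subject through the protocol.**

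- *EC3 applied literally.* If the subject has consented, Section 5.9.2 makes them a screen failure because of the defect that satisfied IC2. If the defect is considered before consent, the subject is simply not offered the study.
- *EC3 set aside for the index defect.* Enrolment breaches the exclusion. No emergency is involved, so Sections 5.14.8 and 5.14.2 do not permit it, and a deviation CRF is required. Classification is also unclear. The intent and attempt definitions in Section 5.9.2 require that eligibility was met, while the procedure-subject definition refers only to undergoing the procedure under the protocol. The subject could fit both the screen-failure and the procedure definitions, and only procedure subjects count toward the enrolment target.

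**4. Try to size the loss.** Let N be the number of ASD-closure candidates and p the share whose defect falls in the first row. Candidates left after the overlap = N × (1 − p). The documents give neither N nor p, so p is taken over its whole range as an assumption:

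- p = 0: N × 1 = N, no loss
- p = 0.5: N × 0.5 = N/2
- p = 1: N × 0 = 0, all lost

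This is a bound and not an estimate. N is open as well: enrolment ends at 40 procedure subjects of any type (Sections 5.2 and 5.9.1), with no minimum per procedure.

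**The case against.** The strongest reply is that there is no contradiction. Inclusion and exclusion criteria apply together, IC2 is necessary but not sufficient, and the literal answer is unique: the subject is excluded. An ablation candidate with LVEF below 30% also meets both IC2 and EC3, and nobody would object. The other ASD types remain available, so the objective can stand beside EC3. To show that EC3 removes most ASD candidates, one would have to know that guideline-indicated closure depends on hemodynamic significance, which the protocol does not say.

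Much of this stands. Formally EC3 prevails, and the documents do not support a claim that it empties the ASD group. The LVEF comparison fails, however: low LVEF is separate from the reason for the ablation, whereas here the excluding condition is the defect to be closed. A unique literal answer is little comfort when it removes subjects from a population the objective names, with no sign that this was meant.

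A second reply is that Section 5.10.1 places the finding of eligibility before consent, so a known ASD would rarely produce a screen failure. That is fair as to frequency. Section 5.10.2 nevertheless verifies eligibility again at the baseline visit, so a screen failure after consent remains possible. Screening out before consent loses the same subject.

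A third reply is that nothing statistical depends on the point: there are no formal endpoints or tests, the sample size is not statistically based, and the analysis is descriptive. That is correct, and it limits how serious the matter is.

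**Conclusion.** The concern holds for subjects whose index ASD is congenital and judged hemodynamically significant. For them IC2 and EC3 turn on the same defect, and no text in the protocol reconciles the two. ASDs judged not significant, and non-congenital ASDs that pass the other criteria, are unaffected.

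The size cannot be established from the documents; it lies between no ASD candidates and all of them. The conclusion assumes only that EC3 is read as written and that some ASD candidates have such a defect. The consequences are limited to who can enter for ASD closure and to avoidable eligibility deviations. No planned estimate or test changes. It should be corrected, but it does not threaten the descriptive analysis.

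**What to change.** Reconcile IC2 and EC3 in both Table 2 (Section 5.8) and the synopsis (Section 5.2), so that the text states whether the defect scheduled for closure counts under the congenital item of EC3. If significance remains part of the criterion, say how it is to be judged, so that sites apply it alike. Keep the objective (Sections 5.2 and 5.5) and the sample-size rationale (Section 5.7) consistent with the choice. Which eligibility rule is right is for the sponsor to decide with the investigators.

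The cost is a wording change to one criterion in two places. Under Section 5.14.9 it needs ethics committee approval, and regulatory approval where applicable. If the objective stays as it is, sample size, data collection and analysis need no change.

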5.9. SUBJECT ACCOUNTABILITY**5.9.1. POINT OF ENROLMENT**

A subject is considered as enrolled when the study-specific Informed Consent Form has been obtained.

A study subject's participation will be considered complete when all protocol required visits have been completed. For subjects who underwent the ablation, LAA or ASD closure procedure, the last protocol required follow-up is at 7 days post procedure. Therefore, subjects who underwent the procedure will be followed from enrolment through the ablation/LAA/ASD closure procedure, hospital discharge, and 7-day follow up. There are no other additional study-related visits required for participating subjects except for those additionally scheduled per physician's decision.

**LUMINIZE_CLINICAL PROTOCOL**

Document ID: VER-DOC-527
Controlled Document: VER-SIGN-3084

Study enrolment will be considered as complete when 40 procedure subjects have been enrolled (see section 'subject classification').

Enrolment in the study is expected to be completed in approximately 6 months. The follow-up for each participant is expected to be approximately 7 days, therefore the total study duration is expected to last approximately 7 months.

Up to 2 sites in Ireland may participate in the study. Enrolment in this study is competitive, there is no limit of enrolments per site.

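### Three procedure settings are named in the objective, but enrolment closes on one pooled count with no minimum per setting and no planned summary by setting, so a named setting could end with few or no cases

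*Combined protocol and SAP*

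**What the plan says.** Section 5.5 opens "The objective of the study is to collect data on the usability and integration of the VERAFEYE System in standard of care" and then lists ablation for typical AFL or AF, LAA closure and ASD closure. The synopsis (5.2) and section 5.7 repeat the list. Section 5.7 gives the reason for the number: "A sample size of 40 subjects was chosen to allow for sufficient feasibility testing and data collection for the ablation, LAA and ASD closure procedures". It adds that the number has no statistical basis.

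The closing rule is pooled wherever it appears:

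- Synopsis: "Enrolment will be considered as complete when 40 subjects have completed the ablation, or LAA/ASD closure procedure".
- Section 5.9.1: "Study enrolment will be considered as complete when 40 procedure subjects have been enrolled".
- Section 5.9.2 defines the counted unit, the procedure subject, as "Any participant who undergoes the ablation/LAA/ASD closure procedure with the VERAFEYE System as imaging system per this study protocol". Any one of the procedures therefore counts equally.
- Section 5.9.2 also still carries a different total: "Enrolment will be considered as complete when 20 procedure subjects have been enrolled".

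Section 5.10.3.3 forbids combining an ablation with a closure, or the two closures with each other. Section 5.12 plans descriptive methods and does not mention a breakdown by procedure type.

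**The concern.** The settings are named one by one in the objective, but nothing in the closing rule ties enrolment to them. Each subject can inform only one setting, and subjects come from the investigators' ordinary patients, so the mix will be whatever the sites happen to treat. Forty ablations with no closures would satisfy the rule.

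At stake is whether the study answers its own question. Usability and workflow integration during a closure involve things that an ablation does not show: the view of the closure-device delivery catheter, imaging after device deployment, and deployment success as the procedural outcome (sections 5.10.3.3 and 5.10.3.4). If results are summarised only in a pool, a setting with few or no cases would not stand out, and the summary would mostly describe the commonest procedure.

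**Working it through.** **The plan's own figure.** The 40 cannot be reproduced. Section 5.7 says it is not statistically based, and the protocol gives no alpha, power, effect size or precision target. The check is therefore of what the pooled rule allows.

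**Inputs.** N = 40 (synopsis, 5.7, 5.9.1). One subject counts for one setting (5.10.3.3). The share p of a given setting among procedure subjects is not in the documents, so it is assumed and varied from 2% to one third, the last being an equal split.

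**Cases in one setting.** Treat the count X as Binomial(40, p):

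- Expected cases = 40p
- P(none) = (1 − p)^40. For p = 5% this is 0.95^40 = 0.129.
- P(fewer than 5) = sum over k = 0 to 4 of C(40, k) p^k (1 − p)^(40 − k)

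| Assumed share p | Expected cases | P(none) | P(fewer than 5) |
|---|---|---|---|
| 2% | 0.8 | 45% | 99.9% |
| 5% | 2.0 | 13% | 95% |
| 10% | 4.0 | 1.5% | 63% |
| 20% | 8.0 | under 0.1% | 8% |
| one third | 13.3 | about 0 | 0.1% |

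Five is only a yardstick here; the documents set no such threshold.

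**All three settings together.** Multinomial with N = 40:

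| Assumed mix | P(some setting has none) | P(some setting has fewer than 5) |
|---|---|---|
| 90/5/5 | 24% | 99.8% |
| 80/10/10 | 2.9% | 88% |
| 70/20/10 | 1.5% | 67% |
| equal thirds | about 0 | 0.2% |

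**If the 20 in section 5.9.2 were applied.** P(none) = (1 − p)^20, which is 36% at p = 5% and 12% at p = 10%. The gap widens.

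**What a given number of cases tells the sponsor.** With m cases in a setting, the chance of seeing at least once a usability problem of true frequency 20% is 1 − 0.8^m. The exact one-sided 95% upper bound after no occurrences is 1 − 0.05^(1/m).

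| m | Chance of seeing a 20% problem | Upper bound after 0 of m |
|---|---|---|
| 3 | 49% | 63% |
| 5 | 67% | 45% |
| 8 | 83% | 31% |
| 10 | 89% | 26% |
| 13 | 94.5% | 21% |

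Thirteen is the largest common minimum that three settings can share within 40, since 3 × 13 = 39.

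**The case against.** The strongest reply is that this is a pilot with no endpoints or tests, a sample size openly declared non-statistical, and imaging data meant for product development. On that view the procedure mix is a sponsor's preference, and any report that gives procedure counts would reveal a shortfall. The first part stands: no error rate, power or efficacy claim is touched. The second depends on the report giving those counts, which section 5.12 does not require.

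Four stronger readings are tempting, and the documents do not support them.

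- A reader might infer that section 5.7 promises 40 is enough for each setting. It says the number was "chosen to allow for sufficient feasibility testing and data collection for the ablation, LAA and ASD closure procedures", which names all three without saying each.
- A reader might blame competitive enrolment. The sentence is "Enrolment in this study is competitive, there is no limit of enrolments per site": it concerns sites, not procedure types. With at most two sites treated one after the other, it may let one site's mix dominate, but the gap comes from the pooled count and the missing minimum.
- A reader might conclude that ablation cases say nothing about closures. Section 5.10.3.3 recommends the home view and a range of anatomical views in all workflows, and the transseptal view in both AF ablation and LAA closure. Much of the image material carries over; workflow integration does so less.
- A reader might take an empty or near-empty setting as likely. At a 20% share or an equal split the problem nearly disappears, and no case mix is reported.

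The binomial model also assumes independent cases at a constant share, whereas procedures run site by site with sponsor staff at every case, so the sponsor may be able to steer the mix informally. Section 5.14.10 lets the sponsor stop a study that fails its goal, but that does not secure any mix. Figures 4 and 5 are not available to this review; the text refers to no count per setting in them.

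**Conclusion.** The point holds as a structural gap. Three settings are named as what the study is to assess, the closing rule is indifferent between them, and no analysis by setting is planned. A setting with a 2% to 5% share would probably end with fewer than five cases (95% to 99.9%) and might well have none (13% to 45%). At 20% or more the risk of having none is under 0.1%. Where the study lies in that range cannot be told from the documents, and the percentages rest wholly on the assumed shares; the gap in the rule itself does not.

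Two features bear on the size. The leftover total of 20 contradicts the 40 elsewhere and would make the gap worse. EC3 excludes congenital cardiac abnormality of hemodynamic significance while IC2 admits patients scheduled for ASD closure; depending on how the two are read together, ASD cases could be fewer, and the passages must be reconciled. The consequence is limited to a part of the objective left unanswered without notice, so this is an inexpensive improvement rather than a defect that undermines the study.

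**What to change.** 1. Keep the total at 40 and reconcile the count of 20 in section 5.9.2 with the synopsis and section 5.9.1.
2. In sections 5.7 and 5.9.1, state a minimum number of procedure subjects for each of the three settings. The documents support no particular figure, so the sponsor should choose and justify it, for instance from the detection table above.
3. Hold the last slots for any setting below its minimum, and state a time after which unfilled slots are released to any setting. Without a release, enrolment could stall in exactly the low-share situation where the minimum matters.
4. In section 5.12, report all results by procedure type, showing typical AFL and AF separately because section 5.10.3.3 gives them different workflows. State that no usability or integration conclusion is drawn for a setting that misses its minimum.
5. Reconcile EC3 with the ASD part of IC2 before fixing an ASD minimum.

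No extra subjects are needed. The costs are a running count by procedure type, possibly slower filling of the last slots, and an amendment that needs ethics committee approval (section 5.14.9).
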